4.2. Exclusion Criteria

Any potential subject who meets any of the following criteria will be excluded from participating in the study:

1. Subjects who are not expected to survive for more than 48 hours.
2. Subjects who have had major thoracic or abdominal surgery in the 6 weeks prior to randomization.
3. Criterion modified per Amendment 2:
 - 3.1. Subjects who are considered by the investigator to be immunocompromised within the past 12 months, whether due to underlying medical condition (eg, malignancy or genetic disorder) or medical therapy (eg, medications other than corticosteroids for the treatment of COPD or asthma exacerbations, chemotherapy, radiation, stem cell or solid organ transplant).
4. Subjects with a known history of human immunodeficiency virus (HIV) or chronic viral hepatitis.
5. Subjects with ALT ≥ 3 times the upper limit of normal (ULN) AND bilirubin $\geq 2 \times$ ULN (direct $> 35\%$) OR ALT $\geq 5 \times$ ULN at screening.
6. Criterion modified per Amendment 2:
 - 6.1. Subjects undergoing peritoneal dialysis, hemodialysis, or hemofiltration or with an estimated glomerular filtration rate (GFR, determined by Chronic Kidney Disease Epidemiology Collaboration [CKD-EPI] equation¹⁵) of < 60 mL/min/1.73m².

$$GFR = 141 * \min\left(\frac{Scr}{\kappa}, 1\right)^\alpha * \max\left(\frac{Scr}{\kappa}, 1\right)^{-1.209} * 0.993^{Age} * sex * race$$

Legend:

Min	minimum of Scr/ κ or 1
max	maximum of Scr/ κ or 1
Scr	serum creatinine measured in mg/dL
κ	0.7 for women, 0.9 for men
α	-0.329 for women, -0.411 for men
Age	measured in years
Sex	1.018 for women, 1 for men
Race	1.159 for black, 1 for white and other

NOTE: The IDMC may recommend to lower the exclusionary GFR limit to < 30 or < 15 mL/min/1.73m² if any available emerging PK data in subjects with GFR ≥ 60 mL/min/1.73m² suggest that ALS-008112 exposure in the setting of moderate (ie, GFR ≥ 30 to < 60 mL/min/1.73m²) or severe (ie, GFR ≥ 15 to < 30 mL/min/1.73m²) renal impairment are projected to remain within an

acceptable range.

In the event a local site is unable to perform a CKD-EPI determination, an alternative methodology for determining GFR is permissible if discussed with and approved by the sponsor.

7. Known allergies, hypersensitivity, or intolerance to ALS-008176 or its excipients (refer to the IB).¹⁶
8. Criterion deleted per Amendment 2
9. Subjects unwilling to undergo mid-turbinate nasal swab procedures or with any physical abnormality which limits the ability to collect regular nasal specimens.
10. Subjects unable to take medications enterally or with a known gastrointestinal-related condition that is considered by the sponsor or investigator to be likely to interfere with study drug absorption.
11. Women who are pregnant or breastfeeding.
12. Criterion modified per Amendment 2:
 - 12.1. Men who plan to father a child while enrolled in this study or within 104 days after the last dose of study drug.
13. Subjects taking any disallowed therapies as noted in Section 8 before the planned first dose of study drug.
14. Criterion modified per Amendment 2:
 - 14.1. Subjects who received prescription medications intended to prevent or treat the RSV infection itself (eg, ribavirin, IV immunoglobulin, palivizumab), an investigational drug, an investigational vaccine, or used an invasive investigational medical device within 30 days or 5 half-lives (whichever is longer) before the planned first dose of study drug or is currently enrolled in an investigational study.
15. Subjects with any condition for which, in the opinion of the investigator, participation would not be in the best interest of the subject (eg, compromise the well-being) or that could prevent, limit, or confound the protocol-specified assessments.
16. Subjects who have used systemic corticosteroids for >7 consecutive days immediately prior to randomization at doses higher than 20 mg/day of prednisone or equivalent.
17. Subject is being treated with extracorporeal membrane oxygenation.
18. Subjects with 1 or more of the following laboratory abnormalities at screening as defined by the Division of Microbiology and Infectious Diseases (DMID) Adult Toxicity Table (see [Attachment 1](#)):
 - Hemoglobin <9.5 g/dL

- Platelet count <75,000/mm³
- White blood cell count <1,000/mm³
- Absolute neutrophil count <1,000/mm³

Note: Retesting of abnormal laboratory values that may lead to exclusion will be allowed once without asking prior approval from the sponsor. Retesting will be performed once within the screening window. Subjects with a normal value at retest may be included.

NOTE: Investigators should ensure that all study enrollment criteria have been met at screening. If a subject's clinical status changes (including any available laboratory results or receipt of additional medical records) after screening but before the first dose of study drug is given such that he or she no longer meets all eligibility criteria, then the subject should be excluded from participation in the study. Section 9.1.2 describes options for retesting. Section 17.4 describes the required documentation to support meeting the enrollment criteria.

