Study ALS-8176-504 determined the absolute bioavailability of ALS-008112 and mass balance of ALS-008176 in healthy adult subjects. Following oral administration of a 375 mg ^{14}C -ALS-008176 solution, 84% of the total administered radioactive dose was recovered in the urine and feces during the 312-hour collection period. Approximately half of the administered dose was recovered within the first 24 hours. Approximately two-thirds of the total radioactivity was recovered in the urine suggesting renal elimination is the major route of elimination for the prodrug and its metabolites. Metabolite profiling and identification confirmed that ALS-008112 and ALS-008144 are the 2 major metabolites in plasma, urine, and/or feces. The absolute oral bioavailability of an oral dose of 500-mg of ALS-008176, measured by the formation of the parent nucleoside analog, ALS-008112 (AUC_{0-last}), was determined to be approximately 60%.

Study 64041575RSV1006 investigated the PK of ALS-008176 after a single oral dose of 1,000 mg in adult subjects with various degrees of impaired renal function. Overall, based on the geometric mean ratios, C_{max} of ALS-008112 was similar in subjects with impaired renal function compared to subjects with normal renal function, and AUC_{0-last} and area under the concentration-time curve from time zero extrapolated to infinite time (AUC_{0-inf}) increased with a decrease in renal function (Table 4).

Table 4: Pharmacokinetic Parameters of ALS-008112 Following a Single Oral Dose of 1,000 mg ALS-008176 in Subjects With Different Degrees of Renal Function

Pharmacokinetic Parameter of ALS-008112	Normal renal function	Mild impaired renal function	Moderate impaired renal function	Severe impaired renal function	End-stage renal disease
n ^a	14	6 ^a	6	6 ^b	6 ^a
C_{max} (ng/mL)	3,258	2,800	4,108	3,721	3,682
AUC_{0-last} (ng.h/mL)	11,659	12,905	18,260	19,105	25,335
AUC_{0-inf} (ng.h/mL)	12,438	14,455	19,550	21,086	30,410

Abbreviations: AUC_{0-last} : area under the concentration-time curve from time zero to the time of the last quantifiable concentration; AUC_{0-inf} : area under the concentration-time curve from time zero extrapolated to infinite time; C_{max} : maximum plasma concentration; eGFR: estimated glomerular filtration rate.

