Given the active nature of the ongoing development program, the IDMC may recommend that one of the dose regimens be removed or one or both of the dose regimens be adjusted based on safety and/or antiviral activity considerations from ongoing studies. Irrespective of the dose, the average projected ALS-008112 plasma exposure ([Table 5](#)) will not exceed a projected average AUC_{0-24h} of 20,000 ng.h/mL, a limit that is 2.5-fold lower than the lowest systemic NOAEL observed in nonclinical toxicity studies.

Treatment Duration

Treatment will last for 5 days as this was the duration of treatment assessed in healthy adult subjects infected with RSV in a human challenge model (Study ALS-8176-502), which demonstrated substantial declines in RSV RNA viral load and improvement in RSV signs and symptoms. The long terminal $t_{1/2}$ of the NTP is anticipated to provide therapeutic levels of the

active NTP beyond the 5-day dose duration. The treatment duration may be extended to up to 10 days if recommended by the IDMC, based on emerging data from the present and other ongoing clinical studies with ALS-008176.

Clinical Outcomes of RSV Treatment

Treatment with ALS-008176 may reduce the severity and duration of RSV signs and symptoms and their impact on functioning, reduce the need for and duration of supportive care (eg, oxygen supplementation, IV fluids, days of hospitalization) and accelerate the subjects' return to pre-RSV health status and HRQoL. The study will compare treatment regimens to evaluate the impact of treatment with ALS-008176 on the clinical course of RSV disease.

Biomarker Collection

Blood samples will be collected for exploratory biomarker analyses (host RNA), on the premise that these markers may play a role in the treatment response, PK, safety of ALS-008176, or the status and change of the RSV-related disease. In addition, leftover mid-turbinate nasal swabs or blood samples collected for other testing may be used for biomarker analysis (eg, proteins including cytokines) if available on the same premise. They may help to explain interindividual variability in clinical outcomes or to identify population subgroups that respond differently to the drug.

Biomarker samples may be used to help address emerging issues and to enable the development of safer, more effective, and ultimately individualized therapies.

Biomarker analyses may be performed upon the discretion of the sponsor and will be reported separately from this study.

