10.2. Discontinuation of Study Treatment/Withdrawal From the Study

Discontinuation of Study Treatment

A subject will not be automatically withdrawn from the study if he or she has to discontinue treatment before the end of the treatment regimen.

A subject's study treatment must be discontinued if:

- The subject withdraws consent.
- The investigator believes that for safety reasons or tolerability reasons (eg, AE) it is in the best interest of the subject to discontinue study treatment.
- The subject becomes pregnant.
- The subject has an eGFR ≤ 30 mL/min/1.73 m² according to the CKD-EPI equation.
- The subject experiences any of the laboratory abnormalities as specified in Section 9.7.1.

If a subject discontinues study drug before the end of the treatment phase, the subject will be encouraged to continue with end-of-treatment and follow-up assessments in accordance with the [Time and Events Schedule](#).

Withdrawal From the Study

Each subject has the right to withdraw at any time for whatever reason without affecting the right to treatment by the investigator. The investigator should make an attempt to contact the subjects who do not return for scheduled visits or follow-up. Although the subjects are not obliged to give reason(s) for withdrawing early, the investigator should make a reasonable effort to ascertain the reason(s) while fully respecting the subject's rights.

A subject will be withdrawn from the study for any of the following reasons:

- Lost to follow-up.
- Withdrawal of consent.
- Death.
- The subject is poorly compliant with study procedures, study drug administration, visits, and assessments, after evaluation and discussion between the investigator and sponsor.

- Decision by the sponsor to stop or cancel the study.
- Decision by the investigator to withdraw subjects.
- Decision by local regulatory authorities and IEC/IRB to stop or cancel the study.

If a subject withdraws from the study before the end of the treatment phase, the subject will be encouraged to continue with end-of-treatment and follow-up assessments in accordance with the [Time and Events Schedule](#).

If a subject is lost to follow-up, every reasonable effort must be made by the investigator/study-site personnel to contact the subject and determine the reason for discontinuation/withdrawal. The measures taken to follow-up must be documented.

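### If the IDMC's option to lower the GFR limit to below 15 were used, every subject enrolled with eGFR 15 to 30 would already meet the mandatory renal stop in Section 10.2

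*Protocol*

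**What the plan says.** Criterion 6.1 in Protocol Section 4.2 excludes subjects on dialysis or hemofiltration, or with a CKD-EPI GFR "of < 60 mL/min/1.73m²". The note beneath it says "The IDMC may recommend to lower the exclusionary GFR limit to" below 30 or below 15 mL/min/1.73 m². The condition is that emerging PK data from subjects with GFR of at least 60 suggest exposure would stay acceptable in moderate impairment (30 to below 60) or in "severe (ie, GFR ≥ 15 to < 30 mL/min/1.73m²) renal impairment". No figure defines acceptable.

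Section 10.2 lists the cases in which "study treatment must be discontinued if" they occur. One is an eGFR of 30 mL/min/1.73 m² or less "according to the CKD-EPI equation". It is written as a status, not as a fall from baseline, and it has no exception for subjects admitted under a lowered limit.

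Two other places bear on the note's basis. Section 1.1 reports a renal impairment study (Table 4) in which ALS-008112 AUC "increased with a decrease in renal function". Section 3.2 caps the projected average AUC0-24h at 20,000 ng.h/mL, "a limit that is 2.5-fold lower than the lowest systemic NOAEL observed in nonclinical toxicity studies".

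**The concern.** An option written in advance for use during the trial should work when it is taken up. Here one of its two settings would admit a band of subjects to whom another section applies a mandatory stop. A site following both rules would randomise and dose such a subject and then have to stop treatment. A site that kept dosing would be setting aside a mandatory safety rule. Dosed subjects with centrally confirmed RSV stay in the ITT-infected set (Protocol Section 11), so forced early stops would enter the primary comparison.

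The secondary concern is the evidence for the decision. The note looks to subjects with GFR of at least 60 and projects downwards, although the same protocol already reports direct data in moderate and severe impairment and states a numerical exposure limit.

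**Working it through.** **1. Overlap of the two rules.** No sample size, power or alpha figure is involved. The check is to intersect the eligible range under each permitted limit with the stop range (eGFR 30 or below). Both rules are in mL/min/1.73 m² and name CKD-EPI.

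| Exclusion limit | Eligible | Newly eligible | Eligible and already meeting the stop |
|---|---|---|---|
| below 60 (in force) | 60 and above | none | none |
| below 30 (option) | 30 and above | 30 to below 60 | exactly 30 only |
| below 15 (option) | 15 and above | 15 to below 60 | 15 to 30 inclusive |

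The band that only the lower option adds, 15 to below 30, lies wholly inside the stop range. Subjects above 30 and below 60 lie wholly outside it.

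**2. Does another section resolve it?** Section 11.12 lists what may change on IDMC recommendation without amendment: doses, regimen, dosing duration and the symptom-onset window. Section 17.1 lists doses or treatment regimen. Neither mentions the GFR limit or the renal stop rule.

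**3. When would the stop apply?** Section 10.2 gives no assessment time. In Part 2 the first scheduled biochemistry after screening is on Day 2 (Time and Events Schedule, footnote v). Creatinine is in the chemistry panel and eGFR is a listed calculation (Section 9.7). So even if the rule is read as on-treatment only, a subject whose renal function has not recovered above 30 meets it at the Day 2 sample.

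**4. Exposure in the bands the note would admit (secondary point).** Inputs:
- Table 4, geometric-type summary AUC0-inf after a single 1,000 mg dose, in ng.h/mL: normal 12,438 (n=14), mild 14,455 (n=5), moderate 19,550 (n=6), severe 21,086 (n=5).
- Table 5, Regimen C average AUC0-24h: 13,215 on Day 1 and 12,100 on Day 5.

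Assumptions: the renal effect is proportional, and the Table 5 average lies between normal and mildly impaired function, the two groups eligible under the present limit.

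Ratios:
- Moderate: 19,550/12,438 = 1.572 against normal; 19,550/14,455 = 1.352 against mild.
- Severe: 21,086/12,438 = 1.695 against normal; 21,086/14,455 = 1.459 against mild.

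Projected AUC0-24h = Table 5 value × ratio, rounded to hundreds:

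| | Day 1 | Day 5 |
|---|---|---|
| Moderate | 13,215 × 1.352 to 1.572 = 17,900 to 20,800 | 12,100 × 1.352 to 1.572 = 16,400 to 19,000 |
| Severe | 13,215 × 1.459 to 1.695 = 19,300 to 22,400 | 12,100 × 1.459 to 1.695 = 17,700 to 20,500 |

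**5. Cross-check without ratios.** Regimen C maintenance is 2 × 500 = 1,000 mg a day. With linear PK, single-dose AUC0-inf at 1,000 mg approximates steady-state AUC0-24h. Normal function gives 12,438 against 12,100 in Table 5, which agrees. Moderate is then 19,550 (19,550/20,000 = 98% of the limit) and severe 21,086 (105%). Both fall inside the overall ranges above.

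**The case against.** The strongest reply is that the conflict is latent and sits behind further steps. Nothing overlaps under the limit in force. The IDMC only recommends, and its recommendations go to the Sponsor Committee. The GFR limit is not among the changes allowed without amendment, and Section 17.1 otherwise requires one, so Section 10.2 could be aligned when the limit is lowered. This stands and limits the weight of the point. It does not remove it, because neither section refers to the other and nothing prompts the alignment.

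A reader might infer more in four ways, and the documents do not support any of them.
- **All newly eligible subjects would be stopped.** Those above 30 and below 60 would not.
- **The stop falls at the first dose.** Section 10.2 sets no time. What follows from its wording is that the qualifying value already satisfies the rule.
- **The dose-response comparison would be diluted by a known amount.** No section says how many subjects would have eGFR 15 to 30; today there are none. Section 10.2 also encourages those who stop drug to continue assessments.
- **Regimen C would exceed 20,000 in these subjects.** The moderate Day 5 range lies wholly below 20,000 and the other three straddle it. The ratios rest on 5 or 6 subjects per impaired group, and AUC0-inf includes exposure beyond 24 hours. Sections 3.2 and 9.9.4 state the limit as an average, not for each renal stratum.

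It is also fair that the 20,000 cap applies throughout the trial, and that nothing in the note forbids the use of Table 4 or of the popPK model, which has creatinine clearance as a covariate (Section 1.1).

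**Conclusion.** The inconsistency between the criterion 6.1 note and Section 10.2 is real and conditional. Its size is none under the limit of 60, the single value 30 under a limit of 30, and every subject with eGFR 15 to 30 under a limit of 15. This rests on reading the stop rule as a status, as it is written, and on the qualifying value being a CKD-EPI value. Criterion 6.1 allows another method with sponsor approval where a site cannot perform CKD-EPI, and for such a subject the match would be less direct.

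On the secondary point, the note's stated basis should be reconciled with Table 4 and the 20,000 limit. The scaled Regimen C exposures, about 16,400 to 20,800 in moderate and 17,700 to 22,400 in severe impairment, are close enough to the limit to make the basis matter. They depend on a proportional renal effect and very small groups, and they do not show that the limit would be breached.

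**What to change.** Reconcile the criterion 6.1 note with Section 10.2 so that no subject who is eligible under the GFR limit in force meets the renal stop rule at baseline. Whether the note, the stop rule or both should change is for the clinical team. The revised text should also say whether lowering the limit needs an amendment, since Sections 11.12 and 17.1 do not list it.

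Separately, reconcile the basis given in the note with the renal-impairment data in Table 4 and the projected-average AUC0-24h limit, and state how the three relate. No new clinical threshold is proposed here.

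The cost is a wording change in two sections. If the sponsor wants something firmer than the scaling above, one simulation by renal function with the existing popPK model would supply it. The possible downside is that an enrolment option may turn out to be narrower than it now reads.

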4.3. Prohibitions and Restrictions

Potential subjects must be willing and able to adhere to the following prohibitions and restrictions during the course of the study to be eligible for participation:

1. Refer to Section 8 for details regarding prohibited and restricted therapy during the study.
2. Agree to follow all requirements that must be met during the study as noted in the inclusion and exclusion criteria (eg, contraceptive requirements).
3. Concurrent administration of medications/use of licensed devices is allowed as supportive therapy per local standard of care, as long as the medication/licensed device will not affect the subject's participation in the study and is in accordance with allowed concomitant therapy.

5. TREATMENT ALLOCATION AND BLINDING

Treatment Allocation

Procedures for Randomization and Stratification

Central randomization will be implemented for both parts of this study. Subjects will be randomly assigned based on a computer-generated randomization schedule prepared before the study by or under the supervision of the sponsor. The randomization will be balanced by using randomly permuted blocks. For Part 1, randomization will be stratified by region (Japan versus non-Japan). For Part 2, randomization will be stratified by region (Japan versus non-Japan) and age (≥ 18 to < 65 years and ≥ 65 years).

The interactive web response system (IWRS) will assign a unique treatment code, which will dictate the treatment assignment and matching study drug kit for the subject. The requestor must use his or her own user identification and personal identification number when contacting the IWRS, and will then give the relevant subject details to uniquely identify the subject.

Blinding

The investigator will not be provided with randomization codes. The codes will be maintained within the IWRS, which has the functionality to allow the investigator to break the blind for an individual subject.

Data that may potentially unblind the treatment assignment (ie, study drug concentrations, study drug preparation/accountability data, treatment allocation, biomarker, or other specific laboratory data) will be handled with special care to ensure that the integrity of the blind is maintained and the potential for bias is minimized. This can include making special provisions, such as segregating the data in question from view by the investigators, clinical team, or others as appropriate until the time of database lock and unblinding.

Under normal circumstances, the blind should not be broken until the unblinded IDMC review (see Section 11.12). The blind will also be broken for the interim analyses (see Section 11.11) or when all subjects have completed the study and the database is finalized. The investigator may in an emergency determine the identity of the treatment by contacting the IWRS. While the responsibility to break the intervention code in emergency situations resides solely with the investigator, it is recommended that the investigator contact the sponsor or its designee if possible to discuss the particular situation before breaking the blind. Telephone contact with the sponsor or its designee will be available 24 hours per day, 7 days per week. In the event the blind is broken, the sponsor must be informed as soon as possible. The date, time, and reason for the unblinding must be documented by the IWRS in the appropriate section of the electronic case report form (eCRF), and in the source document. The documentation received from the IWRS indicating the code break must be retained with the subject's source documents in a secure manner.

Subjects who have had their treatment assignment unblinded should continue to return for scheduled evaluations. Discontinuation of study treatment should be done only for the reasons stated in Section 10.2; unblinding of study treatment should not necessarily lead to study drug discontinuation.

In general, randomization codes will be disclosed fully only if the study is completed and the clinical database is closed. However, if an interim analysis is specified, the randomization codes and, if required, the translation of randomization codes into treatment and control groups will be disclosed to those authorized and only for those subjects included in the interim analysis.

